### Appendix C. Handling of Dates, Incomplete Dates and Missing Dates

Imputation Rules for Partial or Missing Start Dates for Medical History, Procedures, AE, Conmeds (except corticosteroid recorded ended due to steroid tapering), Hospitalization dates.

Start Date		Stop Date						
		Complete: yyyymmdd		Partial: yyyymm		Partial: yyyy		Missing
		< 1 st dose	≥ 1 st dose	< 1 st dose yyyymm	≥ 1 st dose yyyymm	< 1 st dose yyyy	≥ 1 st dose yyyy	
Partial: yyyymm	= 1 st dose yyyymm	2	1	n/a	1	n/a	1	1
	≠ 1 st dose yyyymm		2	2	2	2	2	2
Partial: yyyy	= 1 st dose yyyy	3	1	3	1	n/a	1	1
	≠ 1 st dose yyyy		3		3	3	3	3
Missing		4	1	4	1	4	1	1

1=Impute the date of first dose; 2=Impute the first of the month; 3=Impute January 1 of the year; 4=Impute January 1 of the stop year

Note: For subjects who were never treated (first dose date is missing), partial start dates will be set to the first day of the partial month or first day of year if month is also missing.

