## 2. Objectives, Endpoints and Hypotheses

### 2.1 Objectives and Endpoints/Estimands

Objectives	Endpoints
Primary	

To evaluate the effect of efavaleukin alfa on induction of clinical remission

	

Clinical remission at week 12

Primary Estimand	
Variable: Clinical remission at week 12	
Estimator: Difference in clinical remission rates	
Population: All subjects with moderately to severely active UC with inadequate response, loss of response, or intolerance to at least 1 of the following: conventional therapy, biologics, or targeted small molecules, who are randomized and received at least 1 dose of investigational product.	
Treatments: Each efavaleukin alfa dose group and placebo.	
Intercurrent event – composite variable strategy: Subjects will be considered as not meeting the endpoint if:	

They initiate or increase the dose of UC related protocol-prohibited medication or concomitant UC medication between the date of the screening endoscopy and the week 12 endoscopy.

Discontinuation of investigational product on or prior to the end of induction period.

A colectomy (partial or total) or an ostomy.

	
Secondary	

To evaluate the effect of efavaleukin alfa on induction of clinical response

	

Clinical response at week 12

To evaluate the effect of efavaleukin alfa on induction of endoscopic remission

	

Endoscopic remission at week 12

• To evaluate the effect of efavaleukin alfa on induction of symptomatic remission

	

• Symptomatic remission at week 12

• To evaluate the effect of efavaleukin alfa as induction therapy on combined endoscopic and histologic remission

	

• Combined endoscopic remission and histologic remission of the colon tissue at week 12

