**Baseline medication:**

Baseline medication is defined as any medication with start date on or before study day 1 and ongoing while on study.

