#### Concomitant UC medication:

Following medications will be classified as concomitant UC medication:

- **Oral 5-ASA**
- **Immunomodulators (azathioprine, 6-mercaptopurine, methotrexate)**
- **Oral corticosteroids**

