### **8.3 Handling of Missing and Incomplete Data**

Subjects may have missing specific data points for a variety of reasons. In general, data may be missing due to a subject's early withdrawal from study, a missed visit, or non-evaluability of a specific clinical measurement at its planned clinical visit. Missing data will not be imputed, except for the data points described below.

Non-responder imputation will be used to impute missing data for the following binary endpoints: clinical remission, clinical response, endoscopic remission, symptomatic remission, combined endoscopic and histologic remission, corticosteroid-free clinical remission.

If a subject has missing data for any of these endpoints, (including missing one or more subscores contributing to the endpoint) at any scheduled visit, the subject will be considered as not meeting the endpoint for that specific visit.

Missing data for the following continuous endpoints will be imputed with worst case imputation: change in Geboes score, total Mayo score, partial Mayo score, and individual Mayo subscores.

**Observed subscores will be used in the calculation of total and partial mayo score, where available. If one or more individual subscores is missing at a given post-baseline timepoint, the missing subscore will be imputed using the worst (highest) observed score across all available baseline and post-baseline visits up to week 12. The total/partial mayo score will be calculated using the imputed subscores, along with observed subscores, if available for that visit.**

Laboratory measurements that are below the lower quantification limits will be considered equal to the lower limit of quantification for all analyses unless explicitly noted otherwise.

Incomplete UC diagnosis date will be imputed as follows:

- If day is missing but month and year are present, impute to the last day of the month
- If day and month are missing and year is present, impute to the 31st December of that year

Missing and incomplete dates of medical history, procedures, AE, concomitant medication and hospitalization dates will be imputed as outlined in [Appendix C](#).

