### Imputation Rules for Partial or Missing Stop Dates

Initial imputation

- If the month and year are present, impute the last day of that month.
- If only the year is present, impute December 31 of that year.
- If the stop date is entirely missing, assume the event or medication is ongoing.

If the imputed stop date is before the start date, set stop date to missing.

If the imputed stop date is after the death date, impute as death date.

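### Appendix C can date a stable background UC drug inside the intercurrent-event window, and no planned output isolates the subjects failed that way

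*SAP*

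**What the plan says.** SAP 8.3 sends incomplete concomitant-medication dates to Appendix C: "Missing and incomplete dates of medical history, procedures, AE, concomitant medication and hospitalization dates will be imputed as outlined in" that appendix. The start-date grid there is headed "Imputation Rules for Partial or Missing Start Dates for Medical History, Procedures, AE, Conmeds" and covers hospitalization dates too. It makes one exception among medications: "except corticosteroid recorded ended due to steroid tapering". Code 1 in the grid is "1=Impute the date of first dose". For stop dates, Appendix C adds: "If the stop date is entirely missing, assume the event or medication is ongoing".

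SAP 2.1 and 9.5.2 score a subject as not meeting the primary endpoint if the subject starts or increases a UC-related prohibited drug or "concomitant UC medication between the date of the screening endoscopy and the week 12 endoscopy". SAP 5.1 defines the second group by drug class alone ("Following medications will be classified as concomitant UC medication"): oral 5-ASA, azathioprine/6-mercaptopurine/methotrexate, and oral corticosteroids.

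SAP 9.5.3 carries the same event rule to clinical response, endoscopic remission, symptomatic remission and combined endoscopic and histologic remission. For the Geboes score, the same events trigger worst-case imputation. Table 9-1 and 9.5.2 add a treatment-policy analysis of week 12 clinical remission; Table 9-2 has none for the secondary endpoints.

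**The concern.** Stable background use of these three drug classes is permitted (Protocol 5.1 criterion 107, 6.7.2.1, Appendix 9). The event is meant to catch added treatment. One grid, however, serves adverse events and medications alike. Dating an adverse event to first dose is cautious, because it keeps the event treatment-emergent. Dating a background UC drug to first dose turns a long-standing therapy into one that appears to begin on study.

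A subject observed in remission at week 12 could then be counted as a failure because a date is incomplete, not because treatment changed. What is at stake is the accuracy of the reported rates for the primary and four binary secondary endpoints, and of the Geboes comparison. A reader of the report could not tell how many failures arose this way.

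**Working it through.** No figure in the plan bears on this, and the power text is redacted, so there is nothing to reproduce. The check is a reading of the rules plus date arithmetic.

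**1. Where code 1 applies (Appendix C grid).**

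| Recorded start | Cells with code 1 |
|---|---|
| Month equals first-dose month | 4 |
| Month differs | 0 |
| Year equals first-dose year | 4 |
| Year differs | 0 |
| Wholly missing | 4 |

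That is 3 of 5 rows and 12 cells, all in the columns where the stop date is on or after first dose (complete, month-only or year-only) or missing. A missing stop is read as ongoing, so an ongoing background drug falls in these columns. A start known only to an earlier month or year receives the first of that month or 1 January of that year and is not moved to first dose.

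**2. Is the imputed date inside the window?** Protocol 8.3.1.2 and Table 1-1 place the screening endoscopy 5 to 14 days before day 1. First dose is therefore after that endoscopy and before the week 12 endoscopy. The imputed start is always in the window.

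**3. Is there an exemption?** None appears in SAP 2.1, 5.1, 8.3, 9.5.2, 9.5.3 or Appendix C, apart from the tapered-corticosteroid exception.

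**4. Which stable drugs can reach code 1?** Latest possible start before first dose = stability period (criterion 107) + endoscopy lead time.

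- 5-ASA and oral corticosteroids: 14 + 5 = 19 days, or 14 + 14 = 28 days.
- Immunomodulators: 84 + 5 = 89 days, or 84 + 14 = 98 days.

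*Month-only case.* For 5-ASA and corticosteroids the first dose must fall on the 20th or later (19 days) or the 29th or later (28 days), which is 137 or 29 calendar days of a 365-day year. For immunomodulators it is impossible, since 89 days exceeds any month.

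*Year-only case.* The drug must have been started in the calendar year of first dose. That is possible from 20 or 29 January for 5-ASA and corticosteroids, and from 31 March or 9 April for immunomodulators.

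*Wholly missing case.* Always possible.

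These dates show when a case can occur, not how often it does.

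**5. Size.** With 60 subjects per arm, one affected remitter changes that arm's rate by 1/60 = 1.7 points. A loss in an active arm lowers that arm's difference from placebo by 1.7; a loss in placebo raises every difference by 1.7.

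If a share q of remitters is affected equally in both arms, the difference is multiplied by (1 − q). The design rates are redacted, so as an illustration only take 18.5% versus 8.2%, which Protocol 2.2.1.1 cites for another drug, and assume q from 1% to 5%. The difference of 10.3 points becomes 10.3 × 0.99 = 10.2 to 10.3 × 0.95 = 9.8. Expected remitters lost in an active arm are 60 × 0.185 × q, or about 0.1 to 0.6.

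**6. Would any planned output show it?** SAP 9.6.8 counts users and dose modifications, not intercurrent events or imputed starts. The treatment-policy analysis uses actual week 12 remission whatever the event, so it restores a falsely failed remitter, but it also restores every subject with a true event.

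**The case against.** The strongest reply is that the SAP already treats such a record as background: "Baseline medication is defined as any medication with start date on or before study day 1 and ongoing while on study". An imputed start on study day 1 meets that definition, and SAP 9.4 lists these three classes among baseline medications. This supports the intent but does not settle the rule. The same date also meets the concomitant-medication definition, and the event rule cites neither. Nor would the baseline definition make a safe exemption, since it would also excuse a true start between the screening endoscopy and day 1. Such a start should be rare, because it would breach criterion 107 and waivers are not given.

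Reach is also limited, and this stands. Start dates are to be collected (Protocol 6.7.1, 6.7.2), and data issues are expected to be resolved before final lock (SAP 7.3). Subjects on corticosteroids who are in response or remission on the local read and enter long-term treatment must begin tapering (Protocol 6.7.2.2.3), and records ended for tapering are outside the grid. The corticosteroid route is therefore largely closed for the subjects who matter most.

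Two stronger inferences are tempting. One is that no sensitivity analysis would reflect the problem. The treatment-policy analysis does, for the primary endpoint; what is missing is an analysis that isolates imputed starts, and any such analysis for the secondary endpoints. The other is that subjects were in fact misclassified. The SAP does not say how initiation is derived in programming, and no document shows that such a record exists.

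**Conclusion.** The concern holds as a gap in the stated rules. Taken literally, Appendix C and the event definition together score permitted stable therapy as newly started in three start-date cases, and nothing planned counts or isolates this. The month-only case is narrow for 5-ASA and corticosteroids and impossible for a stable immunomodulator.

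The number of affected records is unknown and probably small, at 1.7 points of an arm's rate per affected remitter. The 9.8 to 10.2 range rests on borrowed rates and an assumed share.

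A reader might infer that the trial's conclusion is at risk. The documents do not support that: p-values are nominal (SAP 9.1), the study had already met futility criteria at the third interim analysis (SAP 11), and no stated decision rule depends on these rates. The effect is on the accuracy and transparency of reported results. It is a low-priority but worthwhile clarification.

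**What to change.** In SAP 9.5.2 and Appendix C, state that a start imputed under code 1 does not by itself count as initiation when data already recorded show use of that drug before the screening endoscopy. Otherwise keep the current conservative rule.

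Set out in writing what counts as evidence, and apply it blind to treatment arm and week 12 outcome. The blinding matters because the check can only turn failures into remitters, and SAP version 3.0 postdates the decision to terminate. The corticosteroid stratum in the IRT is not enough, since it records use at randomization only. Having passed criterion 107 is not enough either, since it applies only to subjects receiving the drug.

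Report by arm the number of subjects whose event rests only on an imputed start. If there are any, repeat the primary and secondary analyses without those events. Leave code 1 unchanged for adverse events.

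The cost is one or two sentences, a little programming, one count per arm, a blinded check of any flagged records, and a repeat analysis only if the count is not zero.

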### Imputation Rules for Partial or Missing Stop Dates

Initial imputation

- If the month and year are present, impute the last day of that month.
- If only the year is present, impute December 31 of that year.
- If the stop date is entirely missing, assume the event or medication is ongoing.

If the imputed stop date is before the start date, set stop date to missing.

If the imputed stop date is after the death date, impute as death date.

### Imputation Rules for Partial or Missing Death Dates

If death year and month are available but day is missing:

- If yyyyymm for the date last known to be alive equals yyyyymm for death date, set death date to the day after the date last known to be alive.
- If yyyyymm for the date last known to be alive is less than the yyyyymm for death date, set death date to the first day of the death month.

- If yyyy-mm for the date last known to be alive is greater than yyyy-mm for death date, assume date last known to be alive is in error, set death date to the first day of the death month.

If month and day are missing and year of death is known:

- If yyyy for the date last known to be alive equals yyyy for death date, set death date to the day after last known to be alive date.
- If yyyy for the date last known to be alive is less than yyyy for death date, set death date to the first day of the death year.
- If yyyy for the date last known to be alive is greater than yyyy for death date, assume date last known to be alive is in error, set death date to the first day of the death year.

If a death date is totally missing:

Set death date to the day after the date last known to be alive. If the date last known to be alive is a partial date, set it to the first day of the month last known to be alive or first day of the year last known to be alive if month is also missing.

#### Appendix D. Mayo Score Categories

Stool Frequency Subscore	Score
Normal number of stools for subject	0
1 or 2 stools more than normal	1
3 to 4 stools more than normal	2
5 or more stools than normal	3
Rectal Bleeding Subscore	Score
No blood seen	0
Streaks of blood with stool less than half of the time	1
Obvious blood (more than just streaks) or streaks of blood with stool most of the time	2
Blood alone passed	3
Endoscopic Subscore	Score
Normal or inactive disease	0
Mild disease (erythema, decreased vascular pattern)	1
Moderate disease (marked erythema, absent vascular pattern, friability, erosions)	2
Severe disease (spontaneous bleeding, ulceration)	3
Physician's Global Assessment	Score
Normal	0
Mild disease	1
Moderate disease	2
Severe disease	3
Mayo Score = Stool Frequency + Rectal bleeding+ Endoscopic Subscore + Physician's Global Assessment	

Note: The Mayo score range from 0 to 12, with higher score of indicating more severe disease. Modified Mayo score excluded Physician's Global Assessment and ranges from 0 to 9. Composite stool frequency and rectal bleeding score ranges from 0 to 6. The original description of the Mayo score included friability in the definition of an endoscopic subscore of 1. Consistent with current clinical practice and regulatory guidance, the study excluded friability from the definition of an endoscopic subscore of 1.

Stool frequency reports the number of stools in a 24-hour period, relative to the normal number of stools for that patient. The reference "normal" stool frequency for that patient will be recorded electronically at the screening visit. The Normal SF (stool frequency) refers to when the patient was in remission or, if the patient has never achieved remission, the reported stool frequency before initial onset of signs and symptoms of ulcerative colitis. Remission refers to a period of time since being diagnosed with ulcerative colitis when the patient is not experiencing any signs or symptoms relating to ulcerative colitis. This period of time may last a few weeks or a few months or may even last several years. The patient will record this electronically as source data in the tablet device at the screening study visit.

#### Appendix E. Visit Date Considerations

- If the visit includes an actual endoscopy performed, then use the bowel preparation date.
- If the visit includes an actual endoscopy performed, but not getting 3 records from the bowel preparation date then use PGA assessment date.
- If the visit does not include an actual endoscopy performed, then use the PGA assessment date.
- If the visit does not include an actual endoscopy performed, but not getting 3 records from the PGA assessment date then use target assessment date.
- If the visit does not include an actual endoscopy performed and PGA assessment are also missing, then use target assessment date.
- If all above scenarios fails, then use worst case imputation.

The target assessment date for that visit should be used per [Appendix B](#) .

For sites located in France, site number 25001, 25002, 25003, 25004, and 25005, if a subject has an Endoscopy date recorded with a missing Bowel preparation date, then Endoscopy date will be considered for the Bowel preparation date. Bowel prep date may be missing as listed French sites may perform enema on the same day as endoscopy date. No imputation will be performed if Bowel preparation date is present.
